BISPECTRAL INDEX MONITORING OF
SEDATION IN SPONTANEOUS VENTILATION.
CLINICAL TRIAL IN SCHEDULED
COLONOSCOPIES

January 28, 2018

Bispectral Index Monitoring of Sedation in Spontaneous Ventilation. Clinical Trial in Scheduled Colonoscopies

SUMMARY:

Objective: To compare the monitoring of anesthetic depth in endoscopy rooms using the BIS monitor versus conventional monitoring as a guide for sedation, allowing to offer the best care in terms of patient safety. For this we must ensure that the patient is comfortable, without pain and in the absence of motor response, creating the ideal conditions for the patient and the endoscopist.

Methodology: Randomized double-blind clinical trial in patients undergoing scheduled colonoscopies in endoscopy rooms of the Galdakao-Usánsolo Hospital. We will compare the percentage of optimal sedation (defined as BIS parameter between 65 and 85 or score on the Ramsay scale 2 or 3) as well as the need for rescue medication and incidence of complications among the experimental group in the that sedation is guided by BIS and the control in which the anesthetist is blind to the BIS result.

Expected results: It is expected that the use of the BIS decreases the chances throughout the colonoscopy in which it is necessary to deepen the level of sedation at the request of the patient (presence of pain or dissatisfaction) and / or the endoscopist (patient maintained movement that prevents the realization of the test). No significant differences are expected in total medication dose and major complications.

HYPOTHESES AND OBJECTIVES:

Main hypothesis: The percentage of adequate sedation in the experimental group, guided sedation by BIS, will be 20% higher than in the control group guided by Ramsay.

Secondary hypotheses:

- 1.- The need for rescue medication would increase in the control group.
- 2.-The incidence of hemodynamic, respiratory and other complications would increase in the control group.
- 3.- The total dose of anesthetic medication will be higher in the control group.
- 4.- Satisfaction with the test will be similar in both groups.

Main objective:

Measure and compare the percentage of superficial sedation between the two groups.

Secondary objectives:

- 1.- Measure and compare the doses of rescue medication necessary between the two groups.
- 2.- Measure and compare the incidence of respiratory, hemodynamic and other complications observed during the performance of the test and relate them to the level of sedation.
- 3.- Measure and compare the dose of hypnotic and analgesic medication used in sedation between the two groups.
- 4.- Compare the level of satisfaction with the test between the two groups.

METHODOLOGY:

- Design: Randomized clinical trial in which the results of two groups of patients are compared.
- Experimental Group (BIS): group of patients in whom sedation is adjusted using as main parameters the information obtained by the BIS sedation monitor (BIS VISTA, Aspect Medical Systems, USA). The BIS target value between 65 and 85, corresponding to a light or moderate sedation, will be considered, noting the parameters obtained at each significant moment of the test.
- Control Group: sedation based on subjective monitoring of the level of sedation, using the Ramsay scale as a reference.

Scope: The endoscopy rooms of the Galdakao-Usánsolo Hospital, which annually performs around 5,000 colonoscopies (4,917 colonoscopies documented in 2016).

Subjects: The reference population is adult patients undergoing a scheduled colonoscopy at the Hospital.

Eligibility criteria:

This target population of the study must meet the following inclusion criteria:

- Patients older than 18 years.
- Scheduled colonoscopy indication.

- Classification of physical status ASA I, II and III, with the exception of patients with lung, kidney and / or liver disease.
- Body Mass Index (BMI) less than 35 kg / m².
- Intact neurological capacity.
- Acceptance to participate in the study after the contribution of written informed consent.

Exclusion criteria:

- Under 18 years old.
- ASA IV.
- BMI greater than 35 kg / m².
- Refusal to participate in the study.
- Allergy to any of the medications used in sedation, or its components.
- Known mental or neurological disease.
- Renal and / or Hepatic Insufficiency.
- Moderate - severe Chronic Obstructive Pulmonary Disease (COPD) or Obstructive Sleep Apnea (SAHS).
- Chronic opiate users.

Sample size calculation: Based on data from a pilot study conducted in our center, we know that the percentage of patients leaving the sedation ranges BIS 65-85 is around 30%. Assuming a percentage of losses of 20% we would need 90 patients per group. It has been calculated with nQuery Advisor v7.0.

ACTING PROTOCOL:

With patients who meet the selected criteria, we will proceed as follows:

- 1) Oral information to the patient of the scientific study to be developed, with completion of the informed consent and delivery of the information sheet.
- 2) Non-invasive monitoring in the corresponding endoscopy room. Continuous electrocardiography, heart rate, respiratory rate, non-invasive blood pressure, transcutaneous pulse oximetry and capnography will be assessed.
- 3) Positioning of the BIS monitoring system sensor (BIS Quatro™ sensor - BIS VISTA™ monitor - Aspect Medical System) in all patients, regardless of the group to which they are

randomized. To do this, the patient's forehead should be carefully cleaned using a gauze pad soaked in alcohol and left to dry. The sensor is then placed following the manufacturer's instructions.

4) Application of oxygen therapy with nasal glasses maximum 5 L / min connected to a capnography line.

5) Administration of anesthetic drugs following the following protocol: Propofol 1% using the TCI system (Target Controlled Infusion) and Remifentanyl (opioid) intravenously. The rhythms of infusion will be adapted according to the anesthesiologist's judgment to achieve the highest possible degree of comfort, tolerance and analgesia of the patient, depending on the different stimuli provoked during the colonoscopy.

6) All patients will be kept under observation in a space annexed to the endoscopy rooms until their recovery and home discharge, as is usual practice in the Unit. The scale of Aldrete will be used to proceed with the discharge, a score higher than 9 being necessary for this. Patients who do not drive should be advised to perform dangerous or precision activities after 6 to 24 hours after sedation.

These values will be recorded in a paper record during the colonoscopy. This information will be transferred to a database to be carried out in collaboration with the Clinical Research Service of the Galdakao-Usánsolo Hospital.

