## **STATISTICAL ANALYSIS PLAN**

A descriptive analysis of the sample will be carried out by means of frequencies and percentages for the categorical variables and by means and standard deviation or median and interquartile range for the continuous variables.

A comparison will be made between the experimental and control groups of the study with respect to superficial sedation (measured by the BIS and Ramsay), as well as the need for rescue medication and incidence of complications. For this, in the case of continuous variables, the Student's test or the nonparametric Wilcoxon test (when normality is not met), and the chi-square or the Fisher exact test (when the expected frequencies are lower than 5) for categorical variables.

Statistical significance will be assumed when  $p < 0.05$ . All statistical analyzes will be carried out using SAS 9.4 software. Copyright, SAS Institute Inc. SAS and all other SAS Institute Inc. product or service names are registered trademarks or trademarks of SAS Institute Inc., Cary, NC, USA.

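### The primary outcome is defined in one way in the Summary, in another in the SAP, and the 90 per group is sized on BIS alone

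*Protocol*

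**What the plan says.** Four places bear on the main outcome, and they use three names for it.

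- **Protocol, Summary (Methodology):** "optimal sedation (defined as BIS parameter between 65 and 85 or score on the Ramsay scale 2 or 3". This is the only explicit definition.
- **Protocol, Hypotheses and Objectives:** the main hypothesis is about adequate sedation, whose percentage in the experimental group "will be 20% higher than in the control group guided by Ramsay". The main objective is to "Measure and compare the percentage of superficial sedation between the two groups". Neither term is defined there.
- **Protocol, Sample size calculation:** from a pilot study, "the percentage of patients leaving the sedation ranges BIS 65-85 is around 30" per cent. Ramsay does not enter.
- **SAP:** the groups are compared on "superficial sedation (measured by the BIS and Ramsay", by chi-square or Fisher's exact test for categorical variables.

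Under Methodology, sedation in the experimental group is adjusted mainly on BIS, with a target of 65 to 85. In the control group it is judged subjectively, "using the Ramsay scale as a reference".

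**The concern.** The SAP should settle which patients count as successes, and it does not. Its wording could mean a joint criterion, an either-scale criterion, or two separate comparisons with no primary one named. Two analysts could follow the documents and reach different primary results from the same data, and the choice could be made after the data are seen.

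The Summary's *or* has a further problem. Each of its two limbs is the guide for one of the groups: BIS for the experimental group, Ramsay for the control group. Each group can therefore qualify on the scale to which it was steered, which weakens the comparison of the two ways of monitoring. An either-scale endpoint is also not the measure on which the sample size was based.

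**Working it through.** **Inputs.** From the Protocol: about 30% of pilot patients leave BIS 65-85, so about 70% stay within it; a 20% difference; 20% losses; 90 per group. From the SAP: significance at p < 0.05. Not stated, and inferred because they reproduce the 90: two-sided testing, 80% power, continuity correction, and a difference of 20 percentage points rather than a relative 20%.

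**Formulas**, with p̄ the mean of the two rates and d their difference:

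- n_u = [1.960·√(2p̄(1−p̄)) + 0.842·√(p1(1−p1) + p2(1−p2))]² / d²
- n_c = (n_u/4)·[1 + √(1 + 4/(n_u·d))]²
- per group = n_c rounded up, divided by 0.8

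**The plan's figure, BIS alone, 70% versus 90%:**

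- n_u = (1.1087 + 0.4610)²/0.04 = 61.6
- n_c = 15.4 × (1 + √1.3247)² = 71.25, so 72
- 72/0.8 = 90, which matches

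A relative 20% (70% versus 84%) gives 155 evaluable and 194 per group, which does not match.

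**The either-scale rule on the same basis.** Suppose that the pilot's 70% is the control rate, and that a share q of the patients outside BIS 65-85 scores Ramsay 2 or 3. The success rates become 0.70 + 0.30q in the control group and 0.90 + 0.10q in the experimental group. The documents give no value for q. Power is the exact binomial power of the continuity-corrected chi-square test at 72 evaluable per group.

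| q control / q experimental | Rates | n_u | n_c | Per group | Power at 72 |
|---|---|---|---|---|---|
| 0 / 0 | 70% v 90% | 61.6 | 71.25, so 72 | 90 | 82% |
| 0.1 / 0.1 | 73% v 91% | 70.3 | 81.05, so 82 | 102.5, so 103 | 76% |
| 0.2 / 0.2 | 76% v 92% | 81.2 | 93.3, so 94 | 117.5, so 118 | 69% |
| 0.2 / 0 | 76% v 90% | 111.8 | 125.7, so 126 | 157.5, so 158 | 53% |
| 0 / 0.2 | 70% v 92% | 48.7 | 57.45, so 58 | 72.5, so 73 | 91% |

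The last two rows show that unequal shares can move the result either way. With no data on how the scales agree, the either-scale difference is bounded only by 90% − 100% = −10 points and 100% − 70% = +30 points.

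**The case against.** The best reply is that BIS is plainly the intended measure. The sizing uses it, the sensor goes on every patient (Acting Protocol, step 3), and the Summary describes "the control in which the anesthetist is blind to the BIS result". Methodology also describes BIS 65-85 as "corresponding to a light or moderate sedation", so the *or* may simply give two descriptions of one state. This stands as a reading of intent. It does not override the only written definition, and the SAP adds Ramsay without saying what it is for.

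Two further points stand. The sample-size sentence reports a pilot rate and does not itself define an endpoint. The Summary gives no unit (patient, reading or time). Scoring by patient, as in the working above, follows the pilot sentence and is not stated in the definition.

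Three stronger readings are tempting, and the documents do not support them:

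- *The trial is underpowered, or the 90 is wrong.* The 90 is right for BIS alone under the inferred inputs. The shortfalls depend on an assumed q. On an uncorrected chi-square basis the needs would be 78, 89 and 103 per group at q = 0, 0.1 and 0.2, so 90 would still suffice at 0.1. Those figures should not be set against a 90 that reproduces only with the correction.
- *The control success rate must be 70% or higher under the either-scale rule.* That needs the pilot's 30% to describe the control condition, which the Protocol does not say.
- *The two groups will be scored on different instruments.* The wording allows this but does not state it.

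It is also fair to say that a BIS-only endpoint favours the experimental group, whose sedation is steered to that range. That limits what the primary result can show.

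**Conclusion.** The inconsistency is real and must be resolved before outcomes are analysed. No text available for review reconciles the Summary's *or*, the SAP's *and*, and a sample size based on BIS alone. The conclusion rests on that textual conflict, and on the fact that the literal *or* lets each group pass on its own guide. It does not rest on the power figures.

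The numerical effect is conditional: 103 per group at q = 0.1 and 118 at q = 0.2, against 90. This assumes that the pilot rate is the control rate, that q is equal in both groups, and that the inferred sizing basis is right. The true loss is unknown and may be nil, and unequal shares could even raise power.

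**What to change.** In the Protocol's Summary and objectives and in the SAP, use one name and one primary endpoint. Suggested content:

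- **Endpoint:** per patient, yes or no, staying within BIS 65-85, scored identically in both groups under the same scoring rule that produced the pilot's 30%. State that rule.
- **Recording:** prespecify the recording moments and apply them to both groups, with BIS recorded in controls while the anesthetist stays blind to it.
- **Analysis:** one primary comparison with the SAP's chi-square or Fisher test. Report Ramsay 2 or 3 as a separate secondary outcome.
- **Sample size:** state the expected rates, power and sidedness behind the 90, and confirm that the pilot's 30% applies to the control condition.

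If the sponsor prefers a composite, define how the scales combine and restate the power from a composite rate.

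**Cost.** Mostly wording, since the sensor is already placed in every patient. No extra patients are needed if the basis was 70% versus 90% as inferred and the pilot rate fits the control condition; otherwise the power statement must be revised. Someone must record control BIS out of the anesthetist's view, and the Protocol names no such person. Ramsay becomes secondary. Because BIS 65-85 is also the experimental group's titration target, the primary conclusion is limited to staying in the BIS range.

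### Major complications are forecast to show no significant difference, but the supplied analysis is a p-value alone, in a trial sized for sedation depth, and secondary hypothesis 2 predicts more complications in the control group

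*Protocol*

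**What the plan says.** The Protocol Summary gives, as part of the objective, "allowing to offer the best care in terms of patient safety". Under Expected results it forecasts: "No significant differences are expected in total medication dose and major complications".

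Under Hypotheses and Objectives, secondary hypothesis 2 reads: "The incidence of hemodynamic, respiratory and other complications would increase in the control group". Secondary objective 2 is to measure and compare these complications.

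The SAP compares the groups on superficial sedation "as well as the need for rescue medication and incidence of complications". The tests are Student or Wilcoxon for continuous variables and "the chi-square or the Fisher exact test (when the expected frequencies are lower than 5) for categorical variables". The decision rule is "Statistical significance will be assumed when" p is below 0.05.

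The sample size calculation in the Protocol's Methodology starts from a pilot finding that "the percentage of patients leaving the sedation ranges BIS 65-85 is around 30" per cent, and concludes: "Assuming a percentage of losses of 20% we would need 90 patients per group".

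The supplied text gives no expected complication rate, no definition of a major complication, no safety margin and no confidence interval for a between-group difference. Part of the SAP was not available for this review, so these absences are established only for the text at hand.

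**The concern.** There are two problems.

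First, the Summary and hypothesis 2 point in different directions. One expects no significant difference in major complications; the other expects more complications in the control group. They could be compatible if major complications were a defined subset of those in hypothesis 2, but no such subset is defined.

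Second, a p-value from a trial sized for another endpoint says little about uncommon events. With few events, p is likely to be 0.05 or more whether or not the arms differ by an amount that would matter. Because patient safety is in the stated objective, readers will look to the complication comparison for a safety conclusion, and the plan gives them no estimate of how large a difference remains possible. This applies in both directions: a true excess with BIS guidance could go unseen, and so could the benefit that hypothesis 2 predicts.

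**Working it through.** **1. Reproduce the plan's own figure.** Inputs from the Protocol: about 30% of patients outside the BIS range, read as 70% adequate in the control group; a gain of 20%, read as 20 points, giving 90%; losses of 20%. Assumed because not stated: two-sided alpha 0.05 and 80% power.

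- Uncorrected: n = [1.960 √(2 × 0.8 × 0.2) + 0.842 √(0.7 × 0.3 + 0.9 × 0.1)]² / 0.20² = 61.6, so 62.
- With continuity correction: n′ = (61.6 / 4) × [1 + √(1 + 4 / (61.6 × 0.20))]² = 71.2, so 72.
- With losses: 72 / 0.8 = 90.

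The stated 90 is matched exactly by the sedation endpoint alone. Other assumptions come close (85% power without correction gives 71, then 89). Nothing in the calculation concerns complications.

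**2. Chance of missing a difference under the SAP's test rule.** Inputs: 72 per group (90 less 20%) or 90 per group; two-sided p < 0.05. In a 2 × 2 table with equal groups, the smallest expected count is half the total number of events. Fisher therefore applies when there are 9 events or fewer in total, and chi-square (taken without continuity correction) otherwise. For true rates p₁ and p₂,

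miss probability = Σ Bin(a; n, p₁) × Bin(b; n, p₂), over all tables (a, b) with p ≥ 0.05.

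The rates are assumptions; the documents give none.

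| Assumed rates | Missed, 72 per group | Missed, 90 per group |
|---|---|---|
| 1% v 3% | 98.9% | 97.6% |
| 1% v 5% | 91.4% | 84.4% |
| 2% v 6% | 89.8% | 84.2% |
| 5% v 10% | 81.0% | 76.6% |
| 2% v 10% | 54.8% | 41.7% |
| 5% v 15% | 47.1% | 36.9% |
| 5% v 20% | 19.1% | 11.0% |

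The first six rows give 47-99% at 72 per group and 37-98% at 90. The range belongs to those pairs. A 10-point rise from a lower base is missed less often: 1% v 11% is missed 33% of the time at 72 and 19% at 90. Using Fisher throughout would overstate the miss rate in the higher-rate rows: 5% v 15% would become 57.8% and 45.3%.

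**3. What particular results would show, at 72 per group.**

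- 0 v 5 events (0% v 6.9%): Fisher p = 2 × (72·71·70·69·68) / (144·143·142·141·140) = 0.058, not significant. At 0 v 6, p = 0.028.
- 0 v 0 events: the Wilson upper limit in each arm is 1.96² / (72 + 1.96²) = 3.84 / 75.84 = 5.1%, so the Newcombe 95% interval for the difference is about -5 to +5 points. At 90 per group it is 3.84 / 93.84, or about ±4 points.
- 0 v 5 events by the same method: the Wilson limits are 0 to 5.07% and 3.00 to 15.25%. The difference of 6.94 points has lower limit 6.94 - √(3.94² + 5.07²) = 0.5 and upper limit 6.94 + (15.25 - 6.94) = 15.2 points. The interval shows how large a difference remains possible, which the p-value does not. It also excludes zero although Fisher gives 0.058, so the SAP should name one interval method in advance.

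**The case against.** The strongest reply is that the plan commits no stated error. The sentence in the Summary is a forecast under Expected results. It is not a success criterion or an equivalence test. The formal hypothesis on complications is one of difference, for which chi-square and Fisher are suitable tests. Low power for rare secondary safety outcomes is usual in a trial sized on another endpoint. All the miss rates rest on assumed rates, and larger differences would usually be found: 5% v 20% is detected 81-89% of the time.

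Most of this stands. A reader might infer that the investigators intend to treat p ≥ 0.05 as proof of equal safety; no text in either document says so. A reader might also infer that the trial would nearly always miss a safety difference, however large; the table shows that this is true only of uncommon events with small absolute differences. The test itself is not at fault.

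What the reply does not remove is that the supplied text offers only a p-value for complications, leaves the limits of a null result unstated, and gives two expectations that are not reconciled.

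**Conclusion.** The point holds as an inexpensive improvement to the safety analysis and a needed reconciliation of two statements. It leaves the primary analysis unaffected. With 72-90 patients per group, a non-significant complication result would by itself be weak evidence of equal safety if events are uncommon. The miss rate is 77-99% for the assumed pairs up to 5% v 10%, falls to 37-55% for 2% v 10% and 5% v 15%, and is 11-19% for 5% v 20%. These figures assume two-sided testing, uncorrected chi-square where Fisher is not required, and complication rates that the documents do not supply.

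The power argument does not extend to the dose half of the Summary sentence: a t-test would miss a 0.5-SD difference only 15% of the time at 72 per group and 8% at 90.

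**What to change.** In the SAP, add to the complication analysis: events and patients per arm, and the risk difference (BIS minus control) with a 95% confidence interval by one named method (Newcombe or exact), reported alongside the existing test. State that the safety conclusion is limited to the excess that the interval excludes, and that p ≥ 0.05 will not be read as equal safety.

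In the Protocol Summary, replace the forecast on major complications with a statement that the difference will be estimated and that the trial is not powered to show equivalence. Define which complications count as major, and reconcile the Summary with secondary hypothesis 2.

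The cost is a few sentences and one extra SAS option, with no added patients or data. The downside is a more modest safety statement.

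### The dose comparison for secondary hypothesis 3 leaves out baseline weight, giving up a modest and nearly free gain in precision, and does not say how the two drugs are handled.

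*Protocol*

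**What the plan says.** Under Hypotheses and objectives, the protocol's secondary hypothesis 3 reads "The total dose of anesthetic medication will be higher in the control group". Secondary objective 3 is to "Measure and compare the dose of hypnotic and analgesic medication used in sedation between the two groups". The Summary predicts something else: "No significant differences are expected in total medication dose and major complications".

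Step 5 of the Acting protocol has patients receive "Propofol 1% using the TCI system (Target Controlled Infusion) and Remifentanyl (opioid) intravenously". It adds that "The rhythms of infusion will be adapted according to the anesthesiologist's judgment", so the cumulative dose depends on how long the infusion runs.

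Eligibility includes "Body Mass Index (BMI) less than 35 kg / m²", which cannot be checked without a weight.

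The SAP's comparison paragraph covers sedation level, rescue drug use and complications; total dose is not on that list. Its method is, "in the case of continuous variables, the Student's test or the nonparametric Wilcoxon test (when normality is not met". The supplied text gives no covariate, no dose unit and no scaling by weight or time.

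**The concern.** Larger patients would be expected to receive more drug, and so would patients with longer procedures. Both sources of variation go into the error term of an unadjusted comparison of total dose. Weight is fixed before randomisation and should already be recorded, so leaving it out gives up precision that costs almost nothing to recover.

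Precision matters here because the protocol makes two opposing predictions about dose. A non-significant result could be taken as support for the Summary when it may only reflect a wide interval. The SAP promises a p-value but no interval estimate, so a reader could not easily tell the two apart.

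A second gap is that a collective total dose has no clear unit when two drugs are given. The plan should say that each drug is compared on its own.

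**Working it through.** **The plan's own figure.** The protocol states 90 per group for the primary outcome. It can be reproduced with 30% v 10% outside the BIS range, two-sided alpha 0.05, 80% power and a continuity correction, which needs 72 per group; then 72/0.80 = 90. The power, the sidedness and the reading of the effect as 20 points are assumptions, since the protocol states none of them. This figure does not bear on dose, for which the documents give no SD, effect size or power. It does give 90 × 0.80 = 72 evaluable patients per arm.

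**Sensitivity of the dose comparison.** With 72 per arm, two-sided 0.05 and 80% power, the detectable difference in SD units is (1.960 + 0.842) × √(2/72) = 2.802 × 0.1667 = 0.467.

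**Model (assumed).** log total dose = log weight + log duration + residual, with independent terms. This takes dose as proportional to weight. The assumed log-scale SDs are weight 0.15-0.25, duration 0.30-0.45 and residual 0.30.

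- Unadjusted SD = √(weight² + duration² + residual²)
- Weight-adjusted SD = √(duration² + residual²)
- Variance removed = weight² / (weight² + duration² + residual²)
- Detectable ratio = exp(0.467 × SD)

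| Weight SD | Duration SD | Unadjusted SD | Adjusted SD | Variance removed | Ratio, unadjusted | Ratio, adjusted |
|---|---|---|---|---|---|---|
| 0.15 | 0.30 | √0.2025 = 0.450 | √0.1800 = 0.424 | 11% | 1.23 | 1.22 |
| 0.25 | 0.30 | √0.2425 = 0.492 | √0.1800 = 0.424 | 26% | 1.26 | 1.22 |
| 0.15 | 0.45 | √0.3150 = 0.561 | √0.2925 = 0.541 | 7% | 1.30 | 1.29 |
| 0.25 | 0.45 | √0.3550 = 0.596 | √0.2925 = 0.541 | 18% | 1.32 | 1.29 |

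Within a row, the detectable log difference falls by between 0.009 (0.262 to 0.253) and 0.032 (0.230 to 0.198).

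**If dose is not proportional to weight.** Suppose dose varies with weight to the power 0.5. Weight then contributes 0.25 × weight² to the variance. In the second row, adjustment removes 0.0156/(0.1800 + 0.0156) = 8%; in the third row, 0.0056/(0.2925 + 0.0056) = 2%. Below a power of 0.5, dividing by kg would add variance. A covariate does not, because its slope is estimated from the data.

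**Dividing by duration as well.** Only the residual SD of 0.30 is left, and the detectable ratio is exp(0.467 × 0.30) = exp(0.140) = 1.15. This is a different quantity: an infusion rate, not a total dose.

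**The case against.** The strongest reply is that nothing here is wrong, only less efficient. Under randomisation the unadjusted test is valid, and chance imbalance in weight is already part of its standard error. Every SD above is assumed. The only clearly safe covariate, weight, moves the detectable ratio by a few hundredths. All of this stands, and it limits the point to a minor improvement on a secondary outcome.

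A reader might infer three stronger things, and the documents support none of them.

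- **That the two drugs are added together.** No text says so. Hypothesis 3 uses a collective term, but objective 3 names hypnotic and analgesic medication, and step 5 lists the two drugs individually. The plan is ambiguous; it does not specify a sum. Part of the SAP was also not in the text supplied for this review and may define the variable.
- **That the comparison is biased by weight or procedure length.** No bias is shown. What is lost is precision.
- **That the ratio of 1.15 is the size of the missed gain.** It depends on dividing by duration, which is measured after randomisation, may differ by arm, and turns total exposure into a rate. Hypothesis 3 is about total dose.

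The objection that dose may not be proportional to weight is a good one against dose per kg. It does not apply to log weight as a covariate.

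**Conclusion.** The point holds as a modest precision and clarity improvement. In the supplied text, dose has no defined variable and no method beyond an unadjusted two-sample test, while a relevant baseline covariate should be available. Under the assumed SDs and near-proportionality, adjusting for weight removes about 7-26% of the variance and lowers the detectable ratio at 72 per arm from about 1.23-1.32 to about 1.22-1.29. The gain is smaller if dose depends less strongly on weight. A null result would still be imprecise after adjustment, so the interval estimate is worth as much as the covariate. The main conclusion of the trial is not affected.

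**What to change.** Add a short paragraph to the SAP:

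- Name dose as an outcome, with its unit, and analyse propofol and remifentanil separately.
- For each drug, regress log total dose on arm with baseline log weight as a covariate. Report the ratio of geometric means with a 95% CI.
- State in advance how a zero dose of either drug would be handled, since the log would be undefined.
- Show dose per kg per minute and procedure duration by arm as supportive description only. Do not use duration as a covariate.

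In the protocol, reconcile the Summary's expectation on total dose with secondary hypothesis 3.

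No extra patients are needed. The cost is a little more analysis work, plus a check that weight is carried into the database and that procedure times are too if the supportive description is wanted.

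### Complications are counted only during the colonoscopy, although every patient is observed until discharge, so an event confined to recovery never enters the safety comparison

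*Protocol*

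**What the plan says.** **Objective.** Protocol, Secondary objectives, item 2: "Measure and compare the incidence of respiratory, hemodynamic and other complications observed during the performance of the test". The same sentence goes on to say that these complications will be related to the level of sedation.

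**Hypothesis.** Protocol, Secondary hypotheses, item 2: "The incidence of hemodynamic, respiratory and other complications would increase in the control group". No time window is attached.

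**Monitoring.** Acting Protocol, step 2, places the listed measurements in one location: "Non-invasive monitoring in the corresponding endoscopy room".

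**Observation.** Step 6 of the Acting Protocol reads: "All patients will be kept under observation in a space annexed to the endoscopy rooms until their recovery and home discharge, as is usual practice". Discharge requires an Aldrete score above 9. The step names no complication to be recorded during this stay.

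**Recording.** Acting Protocol, closing paragraph: "These values will be recorded in a paper record during the colonoscopy". That paper record is what feeds the database.

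**Analysis.** The SAP compares the groups on superficial sedation, "as well as the need for rescue medication and incidence of complications", using a chi-square or Fisher exact test for categorical variables. It gives no window. One part of the SAP was not available for this review.

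**The concern.** Hypothesis 2 is about complications in general, whereas the objective that is meant to address it stops when the test stops. The recording sentence supports the narrower reading independently. Taken literally, a patient who first desaturates or becomes hypotensive in the recovery space is entered as having had no complication, even though staff are present to see the event.

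The Protocol's stated aim is to offer the best care in terms of patient safety. A report that the arms had similar complication rates, or that one arm had fewer, would be read as covering the whole sedation episode. It would in fact cover only the part before the colonoscopy ended. The gap also has to be closed in advance, since recovery events that nobody wrote down may not be recoverable later.

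**Working it through.** **1. Setting the passages side by side**

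| Place | Window for complications |
|---|---|
| Summary (Methodology) | none stated |
| Secondary hypothesis 2 | none stated |
| Secondary objective 2 | during the test |
| Acting Protocol, step 2 (monitoring) | endoscopy room |
| Acting Protocol, step 6 (observation) | continues to discharge; no event recording mentioned |
| Acting Protocol, closing paragraph (recording) | during the colonoscopy |
| SAP | none stated |

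The only passages that state a complication or recording window limit it to the procedure. No available passage collects or compares events in recovery.

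**2. The plan's own sample size, for the group sizes used below**

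The Protocol states 90 per group with 20% losses. With 30% versus 10% outside the BIS range (20% read as percentage points), two-sided 0.05, 80% power and a continuity correction, the two-proportion formula gives 72 per group, and 72 / (1 − 0.20) = 90. Power, sidedness and the correction are assumptions, because the documents do not state them. The figure is driven by the primary sedation outcome, so a wider complication window does not change it.

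**3. What an incomplete count could do (illustration only)**

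The documents give no complication rate. Assume true incidences of 30% (control) and 15% (BIS). Let *f* be the share of affected patients whose only event is in recovery, the same in both arms. The observed incidences are then 30%(1 − *f*) and 15%(1 − *f*). Power is by exact enumeration of two binomials with an uncorrected two-sided chi-square test at 0.05.

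| *f* | Observed | Difference | Risk ratio | Power, 90 per group | Power, 72 per group |
|---|---|---|---|---|---|
| 0 | 30% v 15% | 15 points | 2.0 | 0.679 | 0.592 |
| 0.20 | 24% v 12% | 12 points | 2.0 | 0.557 | 0.475 |
| 0.40 | 18% v 9% | 9 points | 2.0 | 0.425 | 0.353 |

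The ratio does not move, because (1 − *f*) cancels. The absolute difference and the power both fall.

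**4. Sensitivity to the assumed inputs (90 per group, equal loss)**

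- 30% v 15% with *f* = 0.05 or 0.10: power 0.65 or 0.62, against 0.68 with full capture.
- 20% v 10% with *f* = 0, 0.20, 0.40: 0.469, 0.382, 0.291.
- 10% v 5% with *f* = 0, 0.20: 0.24, 0.19. Here power is low mainly because of sample size, not the window.

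**5. Unequal loss**

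If only control-arm patients had recovery-only events, the observed figures would be 24% v 15% (ratio 24/15 = 1.6, power 0.328) at *f* = 0.20, and 18% v 15% (ratio 18/15 = 1.2, power 0.082) at *f* = 0.40. This shows what it would take to distort the ratio. Nothing in the documents shows that it would happen.

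**The case against.** **The window may be deliberate.** The second half of objective 2 relates complications to the level of sedation. The Protocol's Design section has BIS noted at the significant moments of the test, and no BIS or Ramsay reading is planned in recovery. A recovery event could not be matched to a concurrent sedation level. This stands, and it is a good reason to keep the during-test count as its own analysis. It is not a reason to leave recovery events out of the test of hypothesis 2.

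**Step 6 does not show where the risk lies.** A reader might infer from the discharge score and the advice on activities 6 to 24 hours after sedation that the risk falls mainly in recovery. The documents do not support that. They show that supervision and precautions continue after the test, and they give no event rate for either period.

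**The dose argument has two sides.** A reader might also infer that the comparison is biased towards no difference, because hypothesis 3 says "The total dose of anesthetic medication will be higher in the control group" and residual drug would then cause more recovery events in that arm. The Summary, however, expects no significant difference in total medication dose or in major complications. With the documents disagreeing on dose, a difference between arms in recovery events is not established.

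**The power figures rest on assumed rates.** They do, and a patient who also has an event during the test is already counted, so only recovery-only patients matter. If few patients fall in that group, the loss is small.

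**The text may be looser than it reads.** In the recording sentence it is unclear which values are meant; it directly follows the discharge step. The unavailable part of the SAP could define the variables. Any wider definition there would still have to be reconciled with objective 2.

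**Conclusion.** The point holds in a limited form. As the available text stands, complications confined to recovery are left out of the comparison for hypothesis 2, although the observation that would detect them already takes place. The safety count is incomplete, and the hypothesis claims more than the objective measures.

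The number of events missed is unknown. Equal proportional loss in both arms would cost power and shrink the absolute difference without altering the risk ratio. Under the assumed 30% v 15% with 90 per group, power is 0.557 rather than 0.679 at 20% loss, and 0.62 at 10% loss. Bias in the ratio would need recovery events to differ by arm, and that conclusion should not be drawn from these documents.

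Complications are a secondary outcome. The primary sedation comparison and the 90 per group are unaffected. The conclusion rests on a literal reading of objective 2 and the recording sentence, and on the part of the SAP that could be read.

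**What to change.** - **Objective 2:** define the window as complications observed from the first administration of sedation until discharge from the recovery space.
- **Recording sentence in the Acting Protocol:** state that complications are recorded during the colonoscopy and throughout the recovery stay, in the same way in both arms.
- **SAP:** report during-test events, recovery events and the two combined. Use the combined count, one per patient with any event, for hypothesis 2. Keep the during-test count for relating complications to the level of sedation.

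The cost is a wording amendment and a few added lines on the existing paper form, to be completed by recovery staff. No extra visit or procedure is needed, because observation to discharge is already usual practice. Reported complication rates may be slightly higher. The change concerns only what is recorded and analysed, and should be made before data collection.
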